Aim #4: Conduct a pilot randomized controlled trial (RCT) of *Maisha* to examine 1) feasibility and acceptability in an ANC setting, and 2) impact on early retention in PMTCT, HIV disclosure, and constructs of HIV stigma. *Methods:* We will conduct a pilot RCT with 150 women, both HIV-infected (n=25 *Maisha*; 25 Standard of Care, SoC) and HIV-uninfected (n=50 *Maisha*; 50 SoC). Women will be randomized to receive either the SoC HIV testing and counseling, or SoC plus the *Maisha* intervention. Participants will complete a baseline survey and a follow-up survey at 3 months. Surveys will include measures for health outcomes (e.g., HIV care engagement, adherence to ART, depression, HIV testing), stigma outcomes (e.g., anticipated stigma, enacted stigma, internalized stigma), and other secondary outcomes or potential covariates (e.g., partner support, attitudes to ART, intimate partner violence). A subset of 15 HIV-infected intervention patients will participate in a qualitative in-depth interview at 3 months to provide feedback on the intervention. Clinical data will be abstracted from the medical records of participants completing the 3-month survey.

Overview and timeline

This 5-year study (2016-2021) seeks to understand and inform the implementation of the Option B+ protocol for PMTCT care in the Kilimanjaro Region of Tanzania, and develop an intervention to support women who are newly pregnant and being tested for HIV. The work is being completed in diverse clinical settings, using a multi-methods approach informed by the Consolidated Framework for Implementation Research (Table 1).

Table 1: Study timeline

AIMS	METHODS	YEAR 1				YEAR 2				YEAR 3				YEAR 4				YEAR 5				
		1	2	3	4	1	2	3	4	1	2	3	4	1	2	3	4	1	2	3	4	
Aim 1: Examine implementation of B+ for postpartum care engagement	Observations to assess services and fidelity to protocol																					
	Key informant interviews to assess process and barriers																					
	Record review to assess care engagement outcomes (n=512)																					
Aim 2: Identify factors that impact postpartum care engagement	Enroll pregnant women on ART at clinic sites (n=200)																					
	Follow-up interviews at 3m and 6m postpartum with possible additional surveys up to 2 years postpartum																					
	In-depth interviews to explore care engagement process (n=24)																					

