For the full pilot test of *Maisha*, female ANC patients who are interested in enrolling in the study will be orally administered the informed consent by the study researcher. Participants will then complete an interviewer-administered, structured baseline survey. The survey will include questions about demographics, social support, attitudes toward HIV and people living with HIV, HIV testing history, and mental health. Following the baseline survey, participants will be randomized to receive either the control condition (standard of care) or the intervention condition (standard of care + *Maisha*) (Figure 4).

Participants assigned to the control condition will receive the standard of care at the clinic, which includes all standard procedures related to HIV counseling.

Participants assigned to the intervention condition will receive the *Maisha* Session 1 counseling intervention (video, followed by a brief counseling session) immediately following the baseline survey, in the same private meeting space. They will then return to the waiting area to await the standard of care for the first ANC visit (which includes HIV testing). At this time, the study researcher will inform the clinic nurse that the participant is a part of the intervention condition.

Upon completion of the standard of care HIV counseling and testing, participants who are HIV-positive will be escorted by clinic nurses back to the study researcher's office to immediately complete the *Maisha* Session 2 counseling session. At the conclusion of this session, the participant will be invited and encouraged to attend a Session 3 individual counseling session at the same location 1 week later.

3 months after baseline, all HIV-positive participants (expected n=50) and a sub-set of 100 HIV-negative participants will complete a follow-up survey. The survey will explore key constructs reflecting health outcomes (HIV care engagement, adherence to ART, mental health), stigma outcomes (internalized, anticipated, and enacted stigma), and secondary outcomes (social support, partner support, intimate partner violence). This survey will be conducted in a private room and will take approximately 60 minutes.

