Feasibility and acceptability of the intervention and the associated trial will be described by: recruitment and retention patterns, participant satisfaction, fidelity, and implementation cost. Retention will be monitored to calculate the percentage of participants who attend the 1-week *Maisha* session (in intervention) and the 3-month assessment, to document barriers to attendance for participants, and to examine differences between those who attend and those who do not. Participant satisfaction data at the 3-month follow-up will be described, with >80% satisfaction used as a metric of acceptability. Qualitative data will be thematically coded for focus on participants' perceptions of the intervention, suggestions for changes, and feasibility moving forward. The fidelity to the intervention will be assessed by examining the percentage of components from the manualized content that are covered in each session. To estimate the cost of the intervention, we will track the time for training and delivery, as well as actual costs incurred. Qualitative feedback and QA data will be used to revise and improve the curriculum for the future.

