Potential efficacy will be examined by analyzing separate outcomes for HIV-infected and HIV-uninfected women. For HIV-infected women, we are interested in differences between conditions in health outcomes (retention in PMTCT, medication adherence, depression) and stigma (anticipated stigma, internalized stigma and HIV disclosure). For HIV-uninfected women, we are interested in differences between conditions in stigma (attitudes to PLWH and anticipated stigma), as well as willingness to test for HIV in the future. For outcomes where there is a baseline measure, mixed-effects regressions will be used to model pre-post differences within and between arms, using a time by condition model specification (time, condition, and time*condition). Individual-level random intercepts will be used to account for correlation due to repeated measurement. Using a mixed-effects regression approach leaves flexibility to control for baseline outcome values that may not be balanced between groups due to small sample size, and may improve precision of treatment effect estimation. For outcomes where there is no baseline measure, we will examine differences in means or proportions with 95% confidence intervals. If we suspect, a priori, that baseline imbalance in prognostic covariates may be an issue, we will move into a regression framework. Results across outcomes will generate parameter estimates and potential ranges of values to estimate power for a future R01. This analytic approach is consistent with best practices for analysis of pilot feasibility trials. Data analysis will be led by the KCRI statistician and DGHI postdoc. To reduce bias and ensure reproducibility of results, we will discuss analytic approaches and review syntax as a team. All outcome analysis will be reviewed by an external statistician with study condition blinded (see letter from DGHI Research Design Core).

References

1. U.S. Department of State. *PEPFAR blueprint: Creating an AIDS-free generation*. Washington: U.S. Department of State; 2012.
3. Bateman C. Much ado over the new South African PMTCT guidelines. *S. Afr. Med. J.* Apr 2013;103(4):218-221.

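### Clinic staff are told that a woman is in the Maisha arm before she receives the HIV testing and counselling that both arms share, although the only stated use of that knowledge comes afterwards

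*Combined protocol and SAP*

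**What the plan says.** All of this is in the combined protocol and SAP.

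- **Comparison (section 1, Aim #4):** "Women will be randomized to receive either the SoC HIV testing and counseling, or SoC plus the" Maisha intervention. The Phase 6 procedure describes the control side: "Participants assigned to the control condition will receive the standard of care at the clinic, which includes all standard procedures related to HIV counseling".
- **Randomization (Phase 6, Procedure):** "Following the baseline survey, participants will be randomized to receive either the control condition (standard of care) or the intervention condition".
- **After Session 1, intervention arm only (same section):** "They will then return to the waiting area to await the standard of care for the first ANC visit (which includes HIV testing".
- **Disclosure (next sentence):** "At this time, the study researcher will inform the clinic nurse that the participant is a part of the intervention condition".
- **Use of the disclosure (next paragraph):** "Upon completion of the standard of care HIV counseling and testing, participants who are HIV-positive will be escorted by clinic nurses back" to the study office for Session 2.
- **Fidelity (section 10):** "The fidelity to the intervention will be assessed by examining the percentage of components from the manualized content that are covered in each session".
- **Blinding (section 10):** "All outcome analysis will be reviewed by an external statistician with study condition blinded". No other blinding is stated.

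Section 10 compares outcomes between conditions separately for HIV-infected and HIV-uninfected women. It says that the resulting estimates will inform the power calculation for a future R01.

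**The concern.** Maisha is counselling, and so is part of the standard care that both arms receive. The two can substitute for or reinforce each other. A nurse who knows that a woman has just had a counselling session might shorten her own. She might equally give more attention to someone she knows is in the active arm. In either case the standard component would no longer be the same in both arms, and the analysis could not separate that difference from Maisha itself.

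The outcomes exposed are those that counselling at an HIV test could plausibly affect. For HIV-infected women these are retention, adherence, depression, stigma and disclosure. For HIV-uninfected women they are attitudes, anticipated stigma and willingness to test again. A pilot estimate that mixes Maisha with altered standard care would then be carried into the planning of the next trial.

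**Working it through.** This is mainly a question of sequence. The documents give no effect size, SD, alpha or power for the pilot, so there is no planned figure to reproduce.

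**1. Order of events for an intervention woman (Phase 6, Procedure)**

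| Step | Event | Does the nurse need to know the arm? |
|---|---|---|
| 1 | Consent and baseline survey | No |
| 2 | Randomization | No |
| 3 | Session 1 with study staff | No |
| 4 | Return to waiting area; **nurse is told the arm** | No |
| 5 | Standard HIV counselling and testing | No; shared by both arms |
| 6 | Escort to Session 2 if HIV-positive | Yes |

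Disclosure is at step 4 and the need arises at step 6. Step 5, which should be common to both arms, lies between them.

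**2. Safeguards that might make the order harmless**

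- Nurse kept blind, or separate nurses by arm: not stated.
- Record of the content or length of standard counselling by arm: not stated. The fidelity measure covers the manualized Maisha content only.
- Adjustment in the analysis: the model has time, condition and their interaction, with no term for the standard care delivered.
- Blinded review by the external statistician: this protects the analysis and cannot undo a difference in care already given.

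**3. How a difference would enter the result**

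Let Δ be the true Maisha effect on an outcome. Let b_M and b_C be the shifts in mean outcome caused by any change in standard care in the two arms. The observed contrast estimates Δ + (b_M − b_C). Write b = b_M − b_C. It passes into the contrast in full and may be positive or negative.

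**4. Could the pilot data reveal b?**

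Aim #4 plans 25 v 25 HIV-infected and 50 v 50 HIV-uninfected women. For a simple difference of means in SD units, assuming full follow-up, SE = √(2/n).

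- n = 25 per arm: √(2/25) = 0.28, so the 95% half-width is 1.96 × 0.283 = 0.55 SD.
- n = 50 per arm: √(2/50) = 0.20, so the 95% half-width is 1.96 × 0.20 = 0.39 SD.

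A modest b would lie well inside these intervals. More fundamentally, Δ and b cannot be separated at any sample size unless standard counselling is measured.

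**5. Consequence for planning (assumed values only)**

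Assume Δ = 0.3 SD, SD = 1, two-sided alpha 0.05 and 80% power. Suppose the next trial is sized on Δ + b. Then n per arm = 2(1.96 + 0.842)²/(Δ + b)² ≈ 15.7/(Δ + b)².

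| b (assumed) | Apparent effect | n per arm planned | True power at 0.3 |
|---|---|---|---|
| −0.1 | 0.2 | 393 | above 80% (larger than needed) |
| 0 | 0.3 | 175 | 80% |
| +0.1 | 0.4 | 99 | 56% |
| +0.2 | 0.5 | 63 | 39% |

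The table shows how planning responds to b. It is not an estimate of b, about which the documents say nothing.

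**The case against.** The strongest reply is that this is an open behavioural pilot whose first objective is feasibility and acceptability in an antenatal clinic. Efficacy is described only as potential. The plan includes about 40 hours of observation at each pilot site on clinic flow and on fitting study activities into routine care, and telling the nurse suits that aim. On one view, a nurse's response to Maisha is part of its real-world effect. Nurses may also infer the arm from clinic flow, or women may tell them.

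Much of this stands. It limits the harm and rules out any claim that full blinding is achievable. It does not explain why staff should be told before standard counselling when the stated need comes after it. If the nurse's response is meant to be part of the intervention, the plan should say so, because Aim #4 describes the contrast as standard care with and without Maisha.

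Some stronger readings are tempting but unsupported:

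- *The nurse who is told is certainly the one who tests and counsels.* The procedure says only the clinic nurse, then clinic nurses for the escort. The recruitment text for Phase 6 separately names an intake nurse and an antenatal nurse-in-charge. The identity is a natural reading, not a stated fact.
- *Most disclosures are pointless because most women will test negative.* Results are unknown when the nurse is told, so the study could not then select the women who will need Session 2. The fault is in the timing.
- *The start of PMTCT is also affected at that visit.* The visit sequence does not list it, and the Phase 3 interview topics treat antenatal presentation and PMTCT initiation as two time points.

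**Conclusion.** The point holds as an avoidable risk of performance bias. The arm is disclosed before the care that both arms share, the only stated use comes after it, and nothing in the plan blinds the nurse or tracks standard counselling by arm.

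The size and direction of any bias are unknown. The conclusion rests on two assumptions: that the nurse who is told takes part in the standard testing or counselling, and that knowing the arm could change what she does. The documents establish neither. The pilot design figure is not available in the text reviewed and might add detail on the flow.

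A reader might infer that the Maisha effect will be inflated, or that the pilot contrasts will be uninterpretable. Neither follows. Reduced counselling could shrink the contrast, and there may be no change in care at all. The case for acting is that the correction costs almost nothing and the estimates are meant to inform a larger trial.

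**What to change.** Replace the disclosure sentence in the Phase 6 procedure with wording such as:

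> *Study arm is not disclosed to clinic staff before standard HIV testing and post-test counselling are complete. Each enrolled woman, in both arms, carries an identical sealed slip marked with her study ID. The nurse opens the slip only after post-test counselling of an HIV-positive participant, to see whether she is to be escorted to Session 2. All other slips are returned unopened.*

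The slips must look the same in both arms, so that neither their appearance nor their absence reveals the allocation. The wording should also cover women with an established diagnosis, for whom the slip is opened once standard counselling is complete.

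**Cost:** a one-paragraph edit, printed slips and minor handling. Same-day routing to Session 2 is kept.

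**Limits:** some women will still tell the nurse their arm, and care after that visit is not protected. HIV-positive Maisha women become known to staff through Session 2 and may attend Session 3 a week later, while outcomes are measured at 3 months. The pilot report should state this when the between-arm estimates are used for planning.

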Immediately after the 3-month survey, a subset of 15 HIV-positive intervention participants (5 established diagnoses, 10 new diagnoses) will be invited to participate in a qualitative in-depth interview (IDI) to explore their reactions to the intervention with greater nuance. Interviews will be conducted immediately after the survey and will take an additional 60 minutes. The IDI will be conducted in Kiswahili, using a semi-structured guide. Interviews will be audio recorded with participants' permission.

At the conclusion of pilot trial participation, the research nurse will review the medical records of the 150 pilot trial participants who are selected to receive follow-up as part of the study. A structured data extraction form will be used to record key data on HIV care engagement.

2. Subject Selection

Below are the eligibility and recruitment procedures that the KCMC team will use for inclusion of participants by study phase.

[figure not shown]
Phase 1: Key Informant Interviews with Health Care Providers

Eligibility: 30 health care providers: Individuals who are employed at one of the three study clinics and are involved in the care of HIV-infected women who are pregnant or postpartum. These individuals may include nurses, counselors, physicians, data capturers, and managers.

Recruitment: For health care providers, the KCMC PI ([name]), the Duke graduate student and KCMC research nurses will conduct a brief presentation at each of the study clinics. The research nurse and the Duke graduate student will then approach providers individually to invite them to participate in a key informant interview.

Phase 2: Surveys and In-depth Interviews with female patients

Figure 4. Pilot test design
1st ANC appointment

Eligibility: 200 female patients: Women who are ≥ 18 years of age, diagnosed with HIV, prescribed ART, and pregnant at the time of enrollment are eligible to enroll. Participants may either be newly initiating ART during pregnancy, or continuing ART due to an established HIV diagnosis. To ensure the safety of participants and integrity of the data, participants will be excluded if the attending physician determines that the patient has impaired mental status.

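### Retention in PMTCT has no common scoring day in the pilot, and the two accounts of whose records are abstracted disagree, one of them leaving out women who missed the survey

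*Combined protocol and SAP*

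**What the plan says.** Aim #4 (section 1) gives the pilot's second objective as "impact on early retention in PMTCT, HIV disclosure, and constructs of HIV stigma", with retention first. Section 10, Statistical analysis, opens its list for HIV-infected women with "health outcomes (retention in PMTCT, medication adherence, depression". No outcome is labelled primary.

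The record review is described twice.

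- **Section 1, Phase 6, Procedure:** "At the conclusion of pilot trial participation, the research nurse will review the medical records of the 150 pilot trial participants", limited to those "who are selected to receive follow-up as part of the study". It adds: "A structured data extraction form will be used to record key data on HIV care engagement". The form's fields and cut-off are not given.
- **Section 1, Aim #4:** "Clinical data will be abstracted from the medical records of participants completing the 3-month survey".

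On follow-up, Phase 6 says: "3 months after baseline, all HIV-positive participants (expected n=50) and a sub-set of 100 HIV-negative participants will complete a follow-up survey". It gives no tolerance around 3 months. On analysis, section 10 says: "For outcomes where there is no baseline measure, we will examine differences in means or proportions with 95% confidence intervals". Retention would fall under that sentence, since women enrol at their first antenatal visit.

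No section defines being retained in PMTCT, the day it is judged, how late a woman may be before she counts as lost, or how transfers count. The retention percentages in section 10 are attendance at the 1-week *Maisha* session and at the 3-month assessment. That is retention in the study, not in PMTCT care. For the Phase 2 cohort the plan takes care engagement from records when a woman is lost from the study. Phase 6 has no matching sentence.

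**The concern.** There are two separate problems.

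The first is who is counted. A woman who has left PMTCT care is plausibly less likely to return for a survey. If records are opened only for survey completers, the outcome is conditioned on something close to itself. Retention then reads too high, and if survey attendance by women out of care differs between arms, the arm difference is biased even under randomisation.

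The second is when they are counted. A review date is given but no scoring day. Depending on how that date is read, the nurse may have no later entries with which to separate a late woman from a lost one, or may have very different amounts of later record for different women.

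Section 10 says the results will supply parameter values for the power calculation of a future grant, so an error in the retention rate or the difference would carry into that design.

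**Working it through.** **Inputs from the documents.** Pilot size 25 + 25 + 50 + 50 = 150, which reproduces the number of records in Phase 6. HIV-infected women: 25 per arm. Recruitment: about six months (section 2, Phase 6). Survey: 3 months after baseline. The plan gives no expected retention rate, effect size or power for this outcome, so every rate below is an assumption. The 67% echoes the Background's loss of one-third to one-half by six months postpartum, which is a different horizon.

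**1. Abstraction from survey completers only (Aim #4 wording).** Let R be true retention, and c1 and c0 the survey completion rates in retained and non-retained women. Observed retention = R·c1 / (R·c1 + (1 − R)·c0). Records per arm = 25 × (R·c1 + (1 − R)·c0). Take c1 = 0.95 throughout.

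| True R | c0 | Observed | Records per arm |
|---|---|---|---|
| 67% | 0.95 | 67% | 23.8 |
| 67% | 0.50 | 0.6365 / 0.8015 = 79% | 20.0 |
| 67% | 0.20 | 0.6365 / 0.7025 = 91% | 17.6 |
| 80% | 0.50 | 0.760 / 0.860 = 88% | 21.5 |

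Effect on the arm difference:

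- True 67% v 85% (18 points), c0 = 0.50 in both arms: 79.4% v 91.5%, a difference of 12 points.
- The same with c0 = 0.20 in both arms: 90.6% v 96.4%, a difference of 6 points.
- True 75% in both arms, c0 = 0.30 control and 0.70 intervention: control 0.7125 / 0.7875 = 90.5%, intervention 0.7125 / 0.8875 = 80.3%. A true zero reads as −10 points, against the intervention.

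**2. Review at each woman's own survey (one reading of Phase 6).** With a record ending on day 90, visits every 30 days and a 28-day lateness rule (both assumed), a lapse can be confirmed only if the last visit was by day 90 − 30 − 28 = 32. A woman last seen on day 60 is neither clearly retained nor clearly lost. A lenient rule counts her as retained and reads high. A strict rule that requires the day-90 visit counts a woman a few days late as lost and reads low.

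If each record were scored to its own end, survey timing would matter too. With constant loss and 80% retained at 3 months, retention by record length m months is 0.80^(m/3): 86% at 2 months, 80% at 3 and 74% at 4.

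**3. One review at trial end (the other reading).** The first woman enrolled has 6 + 3 = 9 months of record and the last has 3. Look-ahead past month 3 runs from about 6 months to 0, set by enrolment date.

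**4. Precision, for scale.** Half-width of the 95% interval for a difference = 1.96·√(2p(1 − p)/n). With n = 25 per arm it is 26 points at p = 67%, 22 at 80% and 17 at 90%. With n = 20 and p = 80% it is 25 points. Losing five women per arm while retention reads high therefore leaves the interval about as wide as before, so its width gives no warning of the shift.

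**The case against.** A reader might infer that retention is scored on the survey day with no look-ahead, so that it drifts towards 100% in both arms. The documents do not support that. Phase 6 says when records are reviewed, not the period over which they are scored, and dated entries read later can still be scored as of month 3. The extraction form is not in the document and might fix a cut-off. On the trial-end reading nearly every woman has some look-ahead. An upward push needs a lenient lateness rule, and the plan states none.

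A reader might also infer that unequal record length biases the comparison. By itself it should be similar across randomised arms. Bias between arms needs survey attendance or timing that differs by arm, or attendance that depends on retention.

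It is also fair that this is a pilot: feasibility and acceptability come first in Aim #4, no primary outcome is declared, and the illustrated −10 points lies well inside a half-width of 22 to 26 points.

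Three things stand. The document states two different abstraction populations, one of them conditioned on survey completion. No scoring day or lateness rule appears anywhere. And imprecision does not excuse a systematic shift in figures meant for planning a larger trial.

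**Conclusion.** The point holds as a gap in specification plus a conflict between two passages. Aim #4 and the Phase 6 Procedure disagree on whose records are abstracted and must be reconciled.

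If the Aim #4 wording is followed, retention is overstated whenever women out of care complete the survey less often: by about 12 points at 67% true retention with 95% v 50% completion. A true zero difference can read as −10 points if completion among non-retained women is 30% v 70% by arm. These completion rates are assumed, and with equal completion in retained and non-retained women the bias is nil.

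If the Phase 6 wording is followed, no woman is excluded for missing the survey, but there is still no common scoring day, and look-ahead is either absent or uneven. The direction of that error cannot be stated without a lateness rule. This should be settled before abstraction; it does not undermine the pilot's feasibility aims.

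**What to change.** - Abstract dated PMTCT visit and dispensing entries for every randomised HIV-infected woman, whether or not she completed the 3-month survey.
- Do so at a fixed time after her own baseline that is later than the scoring day, for example 6 months.
- Define retention in section 10 and score every woman as of the same day since baseline, for example month 3. State the lateness rule and how transfers count. Use entries after the scoring day only to separate late from lost.
- Amend Aim #4 and the Phase 6 Procedure so that both name this population and this timing.

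The cost is a few sentences and a delay of a few months before the last records are ready, with no further patient contact. The 100 HIV-uninfected women need no later abstraction for this outcome, because section 10 lists no PMTCT retention outcome for them.

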Recruitment: For female patients, the research nurses will work with a specific health care provider in the clinic to identify individuals who are eligible for the study. The health care provider will approach the patient during a clinical appointment to see if she is interested in meeting with a research nurse to learn more about the study. If so, a research nurse will meet with the patient to explain the study and what participation involves, and to offer her the opportunity to participate if she chooses.

Compensation: At each survey, participants will receive 5,000 TSh (~3 USD) for participation.

Phase 3: Focus Group Discussions and In-Depth Interviews with Stakeholders

Procedure: We will conduct focus group discussions and in-depth interviews with the following populations: health care providers (IDIs/FGDs with 5 HIV care providers, PMTCT coordinators, and ANC nurses providing HIV testing); home-based HIV care workers (2 FGDs, 16 participants); HIV-infected pregnant and postpartum women (18 IDIs); and HIV-uninfected pregnant/postpartum women (12 IDIs). These discussions will identify opportunities to improve implementation of the national PMTCT policy to support continuous care engagement in the postpartum period and inform the content and protocol of the *Maisha* intervention. Semi-structured interview guides will be tailored to each group. Questions and probes related to intervention content (video and counseling) will focus on HIV stigma during two time points: presentation to ANC (e.g., HIV testing experience and current counseling, role of stigma upon HIV diagnosis, stigma for women with established diagnoses) and PMTCT initiation (e.g., content of PMTCT counseling, decision about care site, HIV disclosure). Questions and probes related to the study protocol will include: timing of recruitment, consent, and baseline; reactions to a video-based module; desired characteristics of intervention counselors; and strategies for retention. Interviews and FGDs will be audio-recorded with permission, and transcribed and translated into English. Intervention ideas will be further discussed and refined through a community stakeholder meeting.

Phase 4: Medical Record Review

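### Does comparing the arms within HIV-status groups, when the HIV test follows randomisation, call for test uptake to be reported by arm?

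*Combined protocol and SAP*

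**What the plan says.** The order of events is in Section 1, Phase 6, Procedure. Consent and the baseline survey come first, then allocation: "Following the baseline survey, participants will be randomized to receive either the control condition". Maisha women have Session 1 (video and brief counselling) straight after the survey. Of these women the text says: "They will then return to the waiting area to await the standard of care for the first ANC visit (which includes HIV testing"; and then: "At this time, the study researcher will inform the clinic nurse that the participant is a part of the intervention condition". Later: "Upon completion of the standard of care HIV counseling and testing, participants who are HIV-positive will be escorted by clinic nurses back" to the study office for Session 2.

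Section 10 takes the efficacy outcomes by HIV status: "Potential efficacy will be examined by analyzing separate outcomes for HIV-infected and HIV-uninfected women". The HIV-infected outcomes are PMTCT retention, adherence, depression, anticipated and internalised stigma, and disclosure. The HIV-uninfected outcomes are attitudes, anticipated stigma and future willingness to test.

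Testing also appears in two other places. The Overview says the study will "develop an intervention to support women who are newly pregnant and being tested for HIV". Aim #4 says: "Surveys will include measures for health outcomes (e.g., HIV care engagement, adherence to ART, depression, HIV testing", where testing is one example of survey content. Aim #4's named targets are feasibility, acceptability, early retention, disclosure and stigma.

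Section 2, Phase 6, expects about 1000 women to be enrolled to reach 50 who are HIV-infected. Aim #4 gives 25 per arm HIV-infected and 50 per arm HIV-uninfected. Follow-up and record review cover those 150 women only.

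**The concern.** A subgroup defined after randomisation is not protected by it. If Session 1 makes reluctant women more willing to test, the Maisha arm's HIV-infected group gains women whom the control arm would have left untested. If they are also harder to retain, Maisha looks worse than it is; if easier, better. A nurse who knows the allocation could add to this. Phase 3 of Section 1 mentions "ANC nurses providing HIV testing", although nothing says that the nurse who is told is the one who tests.

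An untested woman belongs to neither group and drops out of the efficacy analysis. Section 10's feasibility list covers recruitment, retention, satisfaction, fidelity and cost, but not index-test uptake. A reader would have no direct way to see whether the groups were formed differently in the two arms. The estimates are also meant to help size a later trial.

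**Working it through.** **The plan's own figures.** 25 + 25 + 50 + 50 = 150 women followed, and 50/1000 = 5% expected to be HIV-infected. These agree across sections. The pilot states no power calculation.

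**Who is exposed to the problem.** Women with an established diagnosis are HIV-infected whatever happens at the visit. Only those without one can be moved, and only by accepting or declining the test.

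**Size of the shift, HIV-infected women.** Let k be the share of HIV-infected women already known positive, u0 and u1 the test uptake in control and Maisha, and g the amount by which retention in the extra women tested falls below that of the others. With no true effect,

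shift = −g(1 − k)(u1 − u0) / [k + (1 − k)u1].

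All inputs are assumptions: k from 1/3 to 2/3, and g of 0.2 or 0.4.

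| Uptake, control vs Maisha | Smallest (g = 0.2, k = 2/3) | Largest (g = 0.4, k = 1/3) |
|---|---|---|
| 98% vs 99% | −0.07 points | −0.27 points |
| 95% vs 100% | −0.33 | −1.33 |
| 90% vs 98% | −0.54 | −2.16 |
| 80% vs 95% | −1.02 | −4.14 |

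Worked example, last row: 0.4 × 0.6667 × 0.15 / (0.3333 + 0.6667 × 0.95) = 0.0400/0.9667 = 4.14 points. With only 20% known positive, the same row gives 0.4 × 0.8 × 0.15 / (0.2 + 0.8 × 0.95) = 5.0 points. If the extra women were retained better, the sign would reverse. With equal uptake the shift is zero in this model.

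**Against sampling error.** At 25 per arm and 70% retention (assumed), the standard error is √(2 × 0.7 × 0.3/25) = 13.0 points, so the half-width is 1.96 × 13.0 = 25.4 points. At 80% retention the half-width is 22.2. A shift of 4.14 points is 4.14/13.0 = 0.32 standard errors, so a nominal 95% interval would cover Φ(1.64) − Φ(−2.28), about 94%.

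**HIV-uninfected women.** Here k = 0, so with g = 0.4 a binary outcome shifts by 0.4 × 0.08/0.98 = 3.3 points at 90% vs 98%, and 0.4 × 0.15/0.95 = 6.3 points at 80% vs 95%. The half-width at 50 per arm is 1.96 × √(2 × 0.7 × 0.3/50) = 18.0 points.

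**What the plan already holds.** The baseline survey, before randomisation, records demographics, social support, attitudes, mental health and HIV testing history. Section 10 allows control for baseline outcome values and, for outcomes with no baseline such as PMTCT retention, a move to regression if imbalance in prognostic covariates is suspected. It also follows the CONSORT extension for pilot trials. Stopping at 50 infected women and following 100 uninfected women require results to be known in both arms.

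**The case for a change.** The best case for a change rests on information, not bias. About 1000 women are randomised and 150 analysed. Uptake is the one step between Session 1 and the HIV-status groups that the full randomisation could estimate well. With about 490 women per arm not already known positive (1:1 allocation assumed), the Newcombe 95% interval for 90% vs 98% is 5.1 to 11.1 points; with 95% uptake in both arms the half-width is 2.8 points.

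Counts of infected women could not stand in for it. At 90% vs 98% with k = 1/3, the positives are in the ratio 0.9333 to 0.9867, so 50 cases split 24.3 to 25.7, well inside the chance range of 18 to 32. The record review leaves out about 850 women, so uptake not logged at enrolment may not be recoverable from the planned extraction.

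These facts stand, but they make a case for an extra descriptive outcome. Equal uptake overall would not show that the same kinds of women accepted the test in each arm; baseline covariates by arm within each group address that more directly. Unequal uptake would add a caveat and change no planned estimate. The cost is a new data field for women outside the record review, with consent coverage to be checked. The regression provision is conditional and cannot deal with unmeasured differences, so it helps only in part.

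That the text describes the route back to the study office only for Maisha women carries no weight. The plan needs infected women identified in both arms, and the pilot-design figure is not available to read.

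**Conclusion.** No change is needed. The observation is correct: group membership is partly settled after randomisation, and uptake by arm is not reported. The design explains it. Session 1 is meant to act before the test, and the main HIV-infected outcomes exist only in infected women, so separate analysis is a fair trade-off.

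In HIV-infected women the possible distortion of the retention difference is about 0.1 to 4 points (5 with few known positives), against a half-width of about 25. In uninfected women it stays below 7 points against 18. These sizes rest on assumed uptake, known-positive share and retention gap, because the documents give none of them. They are not an upper limit: a larger uptake gap would give a larger shift. Nothing in the documents suggests that refusal is common or differs by arm, and testing is part of standard care at the visit.

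For a pilot that reports estimates with intervals to inform a later trial, the planned analysis is adequate. Showing known positive, tested and found infected by arm in the CONSORT flow would be sensible reporting that the analysts can choose to do.
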